b) Psychosocial health related to PTSD will be assessed with well validated scales, including PROMIS measures: Positive Affect-Short Form 15 (PA 15a),⁷⁵ PROMIS Satisfaction with Social Roles and Activities (SSRA) – Short Form 4a (PROMIS-SSRA),^{80,81} PROMIS Short Form v1.0- Satisfaction with Participation in Discretionary Social Activities- Short Form 7a (PROMIS SPDSA),^{82,83} PROMIS Companionship – Short Form 4a (PROMIS-C),^{84,85} PROMIS Depression Short-Form 8a,⁸⁷ and the PROMIS Anxiety Short-Form 8a.⁸⁸ Suicide ideation (SI) will be assessed with the Beck Scale for Suicide Ideation.⁸⁹ Quality of life will be assessed with the Veterans RAND 12-Item Healthy Survey,⁷⁶ Resilience will be assessed with the Connor-Davidson Resilience Scale (CD-RISC-10),⁷⁸ and Quality of an individual's relationships will be assessed with the Relationship Scale Questionnaire (RSQ).⁷⁹

c) The exploratory outcome: cellular aging will be assessed by obtaining absolute telomere length analysis.⁹⁰

Aim 2 Outcome Assessment: Dog HRV, is a reliable measure of stress levels.^{59,91} will be measured with the PetPace Collar (<http://petpace.com>). This non-invasive, monitor wirelessly tracks the dog's HRV and a range of physical and behavioral parameters.

Aim 3 Outcome Assessment: Participant attendance and participation in each session will be recorded by the SD trainers. The SD trainers also keep extensive notes on the interactions between the veterans and the dogs. Documentation of unintended consequences such as aggressive behavior (on either part), allergic reactions, fearful behavior (on either part). These logs will be used to assess participation in the SDTP. Exit phone interviews will be used to obtain veterans' perceptions of the SDTP and their outcomes.

Data Analysis Plan

Human Data: Before analyses, data will be cleaned and illustrated graphically. Summary statistics will be calculated, assumptions examined, and transformations applied as needed. Demographics and baseline characteristics (e.g., PTSDSS, gender) will be compared between the SDTP and WLCI groups, and the relevant variables considered as covariates for multivariable longitudinal analyses. SPSS 25 will be used for all analyses. Significance for rejecting the null is set at $p \leq .05$, Bonferroni sequential corrections will be used for multiple comparisons. The intent-to-treat approach will guide hypothesis testing. Separate sets of analyses are conducted for each outcome.

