H1: Participants in the SDTP ($n = 30$) will demonstrate significantly greater improvement in outcomes from week 1 to weeks 4 and 8 than the WLCI ($n = 30$) in: a) PTSD symptom severity; b) stress markers (decreased cortisol, α -amylase, perceived stress; increased IgA, HRV); c) psychosocial health (increased positive affect, QOL, resilience, and relationships with friends and family, satisfaction with social activities and roles, companionship and decreased depression, anxiety, and suicide ideation); and d) exploratory stress marker cellular aging [increased TL, from weeks 1 to 8 only].

Linear mixed models (LMMs) with random intercepts (participant as a random variable) will be used to assess differences in changes in each outcome between the SDTP and WLCI participants, accounting for the correlation with the repeated measurements of each participant, and using all available data. Fixed effects will include group (SDTP or WLCI), week (1, 4 and 8), and their interaction, as well as the relevant covariates. The hypothesized effect of the intervention will be tested with the week by group interaction. Interactions of covariates (e.g. gender and age) with the group and time will be explored to provide information about their influence and for preliminary data to justify formal evaluation (with adequate power) in future studies. The multi-modal assessment in this study will provide the opportunity to explore characteristics that predict benefits.

Dog data: For analyses of data from dogs, demographics and baseline characteristics (e.g., size, gender, age), will be computed. The distributional characteristics of HRV (e.g., normality, outliers and missing) will be explored. Appropriate steps will be used as needed to ensure that applicable assumptions are met. Descriptive statistics will be computed for HRV by week and period (pre, during, and post).

H2: Dogs who participate in the SDTP will not experience increases in stress (decreases in HRV) from the 30 minutes before, to during, and after SDTP sessions. LMMs with random intercepts (dog as a random variable)

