will be used to assess the significance of changes between the three periods, accounting for the correlation within the repeated measurements. Fixed effects will include period [pre, during, post SDTP session] and week (1, 4, 8). The hypothesized effect of the SDTP will be tested by evaluating the contribution of period to HRV. Interactions of dog covariates (e.g., dog gender and age) with period will be explored to evaluate their potential influence and for exploring a need for evaluation of their roles.

H3: Dogs who participate in the SDTP will not experience increases in stress (decreases in HRV) over 8 weeks of the SDTP. The hypothesized effect of the intervention will be tested by evaluating contribution of week to HRV based on the LMM used for aim 2. Interactions of dog covariates (e.g. gender, age) with week will be explored to provide information about their potential influence to inform development of future studies.

Feasibility data: Descriptive statistics will be calculated for number of sessions attended, rates of completion, drop out adverse events, and follow up questions, etc. Effect size estimates will be calculated for each veteran outcome and for dog HRV. They will enhance sample size calculations for a future multi-program RTC.

Missing Data. While complete data are ideal and we will make considerable effort to obtain them, some missingness is likely. Randomness of missingness will be tested. If there is excessive or differential attrition across groups or informative missingness, we will apply sensitivity analysis, such as pattern mixture models for longitudinal data.⁹² If the results differ, we will report both.

References

2. Bureau USC. FFF: Veterans Day 2017: Nov. 11. 2017.

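### H2 and H3 predict no fall in dog HRV, but the planned tests look for a difference, and no rule says how a non-significant result will be read

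*Combined protocol and SAP*

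**What the plan says.** The dog hypotheses are in the Data Analysis Plan of the combined protocol and SAP. H2 states "Dogs who participate in the SDTP will not experience increases in stress (decreases in HRV) from the 30 minutes before, to during" and after the sessions. H3 states that the dogs "will not experience increases in stress (decreases in HRV) over 8 weeks of the SDTP".

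One linear mixed model with a random intercept for dog serves both. It "will be used to assess the significance of changes between the three periods", with period (pre, during, post) and week (1, 4, 8) as fixed effects. For H2, "The hypothesized effect of the SDTP will be tested by evaluating the contribution of period to HRV". For H3, "The hypothesized effect of the intervention will be tested by evaluating contribution of week to HRV", from the same model.

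Two other items concern dog HRV. The Dog data paragraph plans descriptive statistics by week and period. The Feasibility data paragraph plans effect size estimates, whose stated use is sample size work for a later trial. The only decision criterion in the document is p ≤ .05 for rejecting the null. It appears under Human Data, beside the sentence "Bonferroni sequential corrections will be used for multiple comparisons".

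**The concern.** For H1, rejecting the null supports the hypothesis, so the p ≤ .05 criterion fits. H2 and H3 claim the absence of a fall, and the same criterion does not carry over. A significant period or week effect does not by itself separate a fall from a rise. A non-significant one is compatible with no change and with a real fall too small to detect. The plan names the direction of concern but gives no signed contrast, no confidence-limit rule and no reading of non-significance.

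The stake is the animal-welfare conclusion. H2 and H3 are the only dog-welfare statements that are formally tested; aggressive or fearful behaviour and adverse events are only logged or summarised. With the rule left open, a statement that training does not stress the dogs could come to rest on a p-value above .05, with the reading chosen after the results are known.

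**Working it through.** The documents give no HRV variance, expected change, margin or power for dogs, so there is no figure of the plan's to reproduce. What follows is an illustration in residual-SD units.

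**Inputs.** From the documents: 30 dogs, three periods, three weeks, a dog random intercept, p ≤ .05. Assumed: complete data, residual SD 1, independent residuals within dog, two-sided intervals and the sizes of fall.

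**1. How often the period test misses a real fall.** Each period has 30 × 3 = 90 values. Residual df = 270 − 30 − 4 = 236, and the critical F(2, 236) is 3.03. The noncentrality is λ = 90 × Σ(μⱼ − μ̄)², and the miss rate is P[F(2, 236; λ) ≤ 3.03].

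| Fall | Pattern | Σ(μⱼ − μ̄)² | λ | Miss rate |
|---|---|---|---|---|
| 0.3 | during only, or during and post | 0.060 | 5.40 | 0.469 |
| 0.3 | steady from pre to post | 0.045 | 4.05 | 0.585 |
| 0.5 | during only, or during and post | 0.167 | 15.0 | 0.059 |
| 0.5 | steady from pre to post | 0.125 | 11.25 | 0.144 |

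λ depends on squared deviations, so a rise of the same size gives the same values.

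**2. What an interval would show.** For one contrast between two periods, the 95% half-width is t(0.975, 236) × √(2/90) = 1.970 × 0.149 = 0.294. An observed change of exactly zero would therefore leave a fall of up to about 0.29 SD not excluded.

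**3. Does the same hold for week?** Only if a dog's pre, during and post readings in one week share nothing beyond the dog intercept. Suppose instead that their residuals correlate at ρ (assumed 0.2 or 0.4).

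- True standard error of a week contrast: √[2(1 + 2ρ)/90] = 0.176 at ρ = 0.2 and 0.200 at ρ = 0.4. With session-level df of (30 − 1) × 2 = 58 and t = 2.00, the half-widths needed are 0.35 and 0.40.
- Residual variance that the dog-intercept-only model estimates on average: [58(1 + 2ρ) + 178(1 − ρ)]/236 = 0.948 and 0.895. The half-widths it would report are 1.970 × √(2 × 0.948/90) = 0.29 and 1.970 × √(2 × 0.895/90) = 0.28.

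The reported week intervals are thus too narrow. Simulating that model with no true change gives a week-test false-positive rate of about 13% (ρ = 0.2) to 22% (ρ = 0.4) at a nominal 5%. Coverage of the week 8 − week 1 interval is about 83–90%. The period test moves the other way, rejecting in roughly 3% and 1% of runs.

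**The case against.** The strongest reply is that the plan contains no wrong statement, only an unstated interpretation. A study of changes between three periods may well involve pairwise comparisons, whose estimates carry a sign. The hypotheses name the adverse direction. Descriptives by week and period, with effect sizes, would show whether HRV rose or fell. Dog HRV is not the primary outcome, the work partly serves a future trial, and no programme decision is tied to H2 or H3.

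Much of this stands. A reader might infer that the plan cannot tell a fall from a rise; the planned descriptives largely answer that, so the weight lies on how non-significance is read. A reader might also infer that the investigators will take a non-significant result as proof of no stress. No sentence says so; the defect is that none says otherwise. Nor is the dog analysis without power: on the planned design and these assumptions, a 0.5 SD fall is usually detected.

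What does not stand is that the existing material closes the gap. Pairwise comparisons are still tests of difference. The effect sizes are given another purpose. The sequential Bonferroni sentence sits under Human Data, names no dog comparison, and controls error rate rather than direction or the meaning of a null result.

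**Conclusion.** The concern holds. The stated tests cannot by themselves establish H2 or H3, because both hypotheses assert the absence of a fall and the tests look for a difference. On the assumptions above, a modest fall of 0.3 residual SD would be missed by the period test about half the time (47–58%), against 6–14% for a fall of 0.5 SD. These figures scale with an HRV variance that the documents do not give, and missing data would worsen them.

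The figures should not be carried over to H3 without the condition in step 3. If readings within a session are correlated, the planned model makes week contrasts look more precise than they are, and can signal a rise or a fall that is not there.

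The point deserves correction before the dog data are analysed. It does not touch the PCL-5 primary comparison.

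**What to change.** In the Data Analysis Plan:

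- Base H2 on the during − pre and post − pre contrasts, and H3 on the week 4 − week 1 and week 8 − week 1 contrasts, each with a 95% confidence interval.
- Take them from the planned mixed model with a dog-by-week (session) random effect added, so that the week intervals are not too narrow.
- State the reading in advance. An interval wholly below zero is evidence against the hypothesis. One wholly above zero is favourable for that contrast. One that includes zero is reported as no increase in stress detected, with the size of fall not excluded, and not as proof of no increase.
- Say whether the sequential Bonferroni correction applies to these four contrasts.

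The cost is wording and one extra variance component; data collection and the primary analysis do not change. The downside is that H2 and H3 may end inconclusive and the week intervals may be wider. The rule limits the conclusion; it does not create a success criterion for no increase. A formal conclusion of that kind would need a largest acceptable HRV fall, justified before the HRV data are examined. That step is optional, and the documents give no basis for such a margin.

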Service Dog Training Program for Military Veterans With PTSD

NCT03777020

05-30-2023

Protocol

This RCT will gather data from 60 veterans with Post-traumatic stress disorder (PTSD) and 30 service dogs (SDs) in training. Veterans will be recruited and screened for eligibility according to Warrior Canine Connection (WCC) inclusion criteria Humans: 1) military veteran; 2) diagnosis of PTSD; 3) able to give informed consent; and 4) able to understand English. Human Exclusion Criteria: 1) fear of dogs; 2) allergy to pet dander; 3) active substance abuse; 4) active psychosis, or 5) history of animal abuse. Dog Inclusion Criteria: 1) non-aggressive demeanor as evaluated by WCC protocols for evaluating animal temperament; 2) cleared by veterinarian; and 3) up-to date immunizations. Dog Exclusion Criteria: 1) medical holds.

Recruitment/Screening: Recruitment will be via media attention, flyers, social media, and word of mouth.

Procedures: Veterans interested in the participating in the study will be prescreened by a research team member(RTM) for eligibility. Eligible veterans will be invited to participate. If veterans agree to participate after their questions are answered. They will be consented verbally, randomized, and scheduled for their first session with the location dependent on the arm. After informed consent is signed, baseline data will be obtained in an outdoor area at WCC [service dog training program(SDTP) arm] or at another meeting place near the participant's home [wait list control intervention((WLCI) arm)].

Randomization: Participants will be block randomized, according to gender, into the SDTP or WLCI. Group assignments will be generated by a computerized random number table and envelopes will be opened after verbal informed consent. Participants will continue existing therapies and begin any for which they are referred while in the study.

Interventions:

SDTP-Intervention (human): Veterans randomized to the SDTP will be paired with an experienced WCC Mission Based Trauma Recovery (MBTR)-Trainer (MBRT-T) and a SD. One hour training modules will be scheduled once a week for 8 weeks. Participants will come to WCC for all the weekly training modules. The MBTR-T will deliver the prescribed SDTP modules created by WCC. Each session will be fully supervised by a WCC MBTR-T to address any concerns or safety issues that may arise.

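### The dog HRV model has period and week as main effects only, so it neither estimates nor tests whether the session response changes over weeks 1, 4 and 8; a growing response is diluted, not removed

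*Combined protocol and SAP*

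**What the plan says.** The trial plans data from "60 veterans with Post-traumatic stress disorder (PTSD) and 30 service dogs (SDs) in training". In the Data Analysis Plan (Dog data, H2, H3), the dog analysis is one model:

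- Random part: "LMMs with random intercepts (dog as a random variable").
- Fixed part: "Fixed effects will include period [pre, during, post SDTP session] and week (1, 4, 8").
- H2 (stress does not rise from before, to during, to after a session): "The hypothesized effect of the SDTP will be tested by evaluating the contribution of period to HRV".
- H3 (stress does not rise over the 8 weeks): "The hypothesized effect of the intervention will be tested by evaluating contribution of week to HRV based on the LMM used for aim 2".

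The only dog interactions mentioned are exploratory ones between dog covariates and period ("Interactions of dog covariates (e.g., dog gender and age) with period will be explored") or week. The veteran model under H1, by contrast, names its group-by-week interaction and rests the hypothesis test on it. Under Dog data the plan also promises descriptive HRV summaries for each combination of week and period, with no test, contrast or interval attached.

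**The concern.** A model with only main effects of period and week assumes that the drop in HRV during a session is the same size at weeks 1, 4 and 8. H2 then averages the session response over weeks. H3 averages the week trend over all three periods, including the 30 minutes before the session starts. Whether dogs react more strongly to sessions as the weeks pass lies between the two hypotheses and is not estimated by either.

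This matters because H2 and H3 both claim that stress does not increase. A weak or non-significant result could be taken as support for the dogs' welfare when it partly reflects averaging. The dog HRV effect sizes are also meant to inform the sample size of a later trial, so a diluted estimate would carry forward.

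**Working it through.** The plan gives no power, effect size or variance for dog HRV, so there is no figure of its own to reproduce.

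**Inputs from the documents.** 30 dogs, 3 periods, 3 weeks, significance level .05. That is up to 30 × 9 = 270 records.

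**Assumptions.** Complete data; one session per dog per assessed week; no multiplicity adjustment; only the during-session period is affected.

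**Dilution (needs no variance).** Let the during-session dip be 0, d/2 and d at weeks 1, 4 and 8.

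- H2, during minus pre: (0 + d/2 + d)/3 = d/2.
- H3, week 8 minus week 1: d/3, because one period in three moves.
- With d = 0.6: H2 estimates 0.3 and H3 estimates 0.2, against a true week-8 dip of 0.6.
- A constant dip of 0.3 at every week also gives H2 = 0.3. H2 cannot tell the two patterns apart.

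**Power for dips of 0, 0.3 and 0.6.** Signal sums of squares:

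- Period: 3 × 30 × (0.01 + 0.04 + 0.01) = 5.4.
- Week: 3 × 30 × (0.01 + 0 + 0.01) = 1.8.
- Interaction: 30 × 0.12 = 3.6.

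Write Vp for dog-by-period variance, Vs for session (dog-by-week) variance and Ve for residual variance. The correct error terms are Ve + 3Vp for period, Ve + 3Vs for week and Ve for the interaction. Each noncentrality is signal divided by error, with F tests on (2, 58), (2, 58) and (4, 116) degrees of freedom. The two planned tests are then independent, so the chance that both miss is (1 − H2 power) × (1 − H3 power).

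| Assumed variances | H2 | H3 | Interaction | Both planned tests miss |
|---|---|---|---|---|
| A: dog .5, Vp .1, Vs .2, Ve .3 | 5.4/0.6 = 9.0: 75% | 1.8/0.9 = 2.0: 22% | 3.6/0.3 = 12.0: 78% | 0.25 × 0.78 = 20% |
| B: dog .5, Ve .5 | 10.8: 82% | 3.6: 36% | 7.2: 53% | 0.18 × 0.64 = 11% |
| C: dog .3, Ve .7 | 7.7: 68% | 2.6: 27% | 5.1: 39% | 0.32 × 0.73 = 24% |

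B and C sum to 1 and A to 1.1. Dog variance cancels from every within-dog test, so A gives the same results with dog variance .4 and a total of 1. In set A the single contrast, the change from week 1 to week 8 in during minus pre, has 83% power.

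**The planned random part.** Under set A, a model with only a dog intercept pools the three error strata once the interaction is added: (58 × 0.6 + 58 × 0.9 + 116 × 0.3)/232 = 121.8/232 = 0.525. The interaction is then tested against 0.525 instead of 0.3, and its simulated power falls to about 40%. The week test is too liberal, because its true error is 0.9; its simulated type I error is about 17%.

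**Stable against growing, set A.** H2 has about 75% power for a constant 0.3 dip and the same for the growing one. The week test separates the two at 22% against its 5% null rate; the interaction separates them at 78% against 5%.

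**Other patterns, sets A to C.** For a dip of 0.6 at week 8 only, H2 and H3 each estimate 0.6/3 = 0.2. Both miss in about 29 to 44% of trials, and the interaction detects it in about 51 to 90%. If the response changes sign (−0.3, 0, +0.3), H2 estimates zero and both miss in about 61 to 75%.

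**The case against.** A reader might infer that a growing response is averaged away and that both planned tests are blind to it. The documents do not support that. A response that starts near zero and grows in one direction lowers both the during-session mean and the week-8 mean, so each test keeps part of it. In set A the planned pair misses 20% of the time and the interaction alone about 22%; in sets B and C, H2 by itself has more power than the interaction. The comparison is not quite like for like, since two unadjusted tests carry roughly 10% type I error against 5%. H2 loses the signal entirely only if the response changes sign over the weeks, and both tests lose it only if the other periods offset it as well.

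Nor is 22% against 78% the gain from adding one fixed effect to the planned model. It compares H3 alone with the interaction, leaves out H2, uses the variance set most favourable to the interaction, and needs an error term that the plan does not specify.

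Two further points stand in part. The planned summaries by week and period would show a widening dip to anyone who looked, though without a test or interval. And the tested terms do match the wording of H2 and H3: neither hypothesis mentions a changing session response.

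What remains is that a significant H2 does not answer the question about the 8 weeks, and no planned estimate does so for the session response.

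**Conclusion.** The concern holds in a limited form. As written, the dog model cannot estimate or test change in the session response over weeks 1, 4 and 8. It reports a steadily growing during-session dip at a half (H2) and a third (H3) of its week-8 size. That arithmetic needs only the assumption that the during-session period alone is affected. The power figures rest on assumed variances and dips and should be read as ranges: for the growing dip, about 68 to 82% for H2, 22 to 36% for H3, 39 to 78% for the interaction, and 11 to 24% for both planned tests missing.

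The case for change is interpretive more than a matter of power. The planned analysis may well flag some stress, but it cannot distinguish a stable mild response from a growing one, and its hypotheses are framed so that a diluted result could be read as reassurance. This is a worthwhile, low-cost improvement, not a defect that invalidates the dog analysis.

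**What to change.** 1. Add period-by-week to the fixed effects of the dog model.
2. Report during-minus-pre and post-minus-pre contrasts at weeks 1, 4 and 8 with 95% confidence intervals.
3. State the change in those contrasts from week 1 to week 8 as part of H3.
4. Obtain the right error term, either by computing the change as a within-dog contrast (one value per dog) or by adding dog-by-week (session) and dog-by-period random effects. Adding the fixed effect alone to the intercept-only model is not enough if those variances are present.
5. Keep the period and week main effects as the averaged results for H2 and H3.

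The cost is four fixed-effect degrees of freedom among up to 270 records, a little more analysis and a change of wording. No new data are needed.

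### The only missing-data sensitivity analysis is conditional on triggers that are undefined or, for informative missingness, cannot be settled by the planned test; it should always be run and reported for PCL-5.

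*Combined protocol and SAP*

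**What the plan says.** The H1 paragraph of the Data Analysis Plan sets a random-intercept linear mixed model, "accounting for the correlation with the repeated measurements of each participant, and using all available data". For missing data, the plan expects some loss and then takes three steps, all in the Missing Data paragraph:

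- A test: "Randomness of missingness will be tested". The test is not named.
- A condition: "If there is excessive or differential attrition across groups or informative missingness, we will apply sensitivity analysis". Pattern mixture models are given as an example of that analysis, with a reference to their use in SPSS.
- A reporting rule: both results appear only where they disagree.

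The plan gives no expected dropout rate, no cut-off for excessive or differential attrition, no rule for declaring missingness informative, and no identifying assumption or shift range for the pattern mixture model. No other missing-data sensitivity analysis appears in the document.

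**The concern.** A likelihood-based mixed model on all available data is valid when data are missing at random: given what was observed, dropout does not depend on the unseen values. Informative missingness is the failure of that assumption, and the pattern mixture model is there to probe it. The plan makes the probe wait for evidence that the observed data cannot supply.

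The design makes the issue more than formal. Veterans in the service dog training program (SDTP) travel to the site every week for eight weeks, while the wait list control intervention (WLCI) is taken online from home or a chosen place. Burden differs by arm, so dropout related both to symptoms and to arm is plausible. If SDTP veterans who leave are doing worse than their earlier scores predict, the PCL-5 contrast is biased in favour of SDTP. The effect sizes are also meant to inform sample size for a later trial, so a bias would carry forward even without a significant result.

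**Working it through.** The plan states no figure for dropout, power or the trigger, so there is none to reproduce. The check has four steps.

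**Inputs from the document.** The trial has 60 veterans ("This RCT will gather data from 60 veterans with Post-traumatic stress disorder (PTSD"), 30 in each arm ("than the WLCI ($n = 30"). The level is 0.05 ("Significance for rejecting the null is set at $p \leq .05"), taken here as two-sided because the plan does not say. Visits are at weeks 1, 4 and 8.

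**Inputs assumed.** Dropout rates, within-person correlation (0.6), how far dropouts depart from prediction, and any cut-off for excessive attrition.

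**1. Can the planned test settle informative missingness?** Not from observed data. A test can compare veterans who stay and leave on scores already seen, and so reject missing completely at random. It says nothing about dependence on the unseen score. A simulation of 3,000 trials per scenario shows this (30 per arm, no true effect). Where week-8 dropout depended only on the part of the week-8 value not predicted by weeks 1 and 4, a test of the observed means rejected in 4-6% of trials. That is about its nominal 5%.

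**2. Power of a differential-attrition test, if one is used.** Exact Fisher power, 30 v 30, obtained by summing binomial probabilities over all tables with p at or below 0.05:

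| True dropout | Power |
|---|---|
| 10% v 20% | 10% |
| 15% v 30% | 19% |
| 20% v 40% | 30% |
| 10% v 30% | 37% |
| 10% v 40% | 71% |

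With 3 of 30 lost in one arm, Fisher reaches 0.05 only at 11 of 30 in the other.

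**3. What an unflagged pattern could cost.** Assume that 3 of 30 are lost in WLCI with no departure from prediction, and that SDTP dropouts are worse than predicted by a shift d, in SD units.

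- Bias = (SDTP dropout share) × d.
- SE of the difference in change = √(2(1 − 0.6)) × √(1/n1 + 1/n0) = √0.8 × √(1/n1 + 1/n0), where n1 and n0 are the SDTP and WLCI completers.
- Type I error = Φ(−1.96 + bias/SE) + Φ(−1.96 − bias/SE).

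*6 of 30 lost in SDTP:* n1 = 24, n0 = 27, SE = 0.251. Fisher for 6 v 3 gives p = 0.47.

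- d = 0.5: bias 0.2 × 0.5 = 0.10 SD, type I error 6.8%.
- d = 0.8: bias 0.2 × 0.8 = 0.16 SD, type I error 9.8%.

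*9 of 30 lost in SDTP:* n1 = 21, n0 = 27, SE = 0.260. Fisher for 9 v 3 gives p = 0.10.

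- d = 0.8: bias 0.3 × 0.8 = 0.24 SD, type I error 15.2%.
- d = 1.0: bias 0.3 × 1.0 = 0.30 SD, type I error 21.1%.

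This is a normal approximation on change scores, not a refit of the planned model.

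**4. How often would the analysis run?** This depends on the cut-off. Suppose excessive meant at least 20% lost overall, alongside the two tests above at 0.05. In the simulated scenarios the analysis would then run in 10-17% of trials at 12-13% dropout, 36-51% at 17-19%, and 71-85% at 22-24%.

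**The case against.** The plan deserves credit for naming pattern mixture models and for joining its three triggers with an or. Excessive attrition is naturally an overall rate, to which power does not apply; step 4 shows that with a 20% cut-off and dropout a little above it, the analysis would usually run. Nor does the plan say that attrition will be judged by a p-value, or that the test of randomness alone decides whether missingness is informative. Attendance logs, trainers' notes, exit interviews and descriptive dropout rates are also planned and could inform a judgement.

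These points stand, and they limit the claim. A reader might infer that the sensitivity analysis will often be skipped when it is needed. The document does not support that, because the frequency turns on a cut-off and a dropout rate that it does not give. A reader might also attach the bias figures to any trial with heavy SDTP dropout. That goes too far as well: with no WLCI losses, 6 v 0 and 9 v 0 give Fisher p = 0.024 and 0.002, so even a strict test of differential attrition would trigger the analysis. The illustration therefore uses 3 WLCI losses, where that test stays silent.

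The objection does not repair the rule. The other sources of evidence are not linked to the trigger and could not establish informative missingness with certainty. Without thresholds, whether to run the analysis is decided after the data are seen.

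**Conclusion.** The point holds. That the test of randomness cannot settle informative missingness, and that a non-significant result does not support missing at random, needs no numerical assumption. That the attrition triggers lack thresholds is plain from the text. Their low power (10% and 37% for the two gaps starting at 10%) applies only if they are read as Fisher tests at 0.05.

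The size of the harm is illustrative: a bias of 0.10-0.16 SD with type I error of about 7-10%, or 0.24-0.30 SD with about 15-21%. It rests on the assumed correlation, losses and shifts, with the whole departure placed in SDTP. It shows that a pattern the attrition test would pass can matter; it does not predict what this trial will see.

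**What to change.** In the Missing Data paragraph, remove the conditional trigger. State that a pattern mixture sensitivity analysis for PCL-5 will always be run and reported beside the primary mixed model, whether or not the results differ. Specify its form in advance. One option is delta adjustment with a pre-stated range of shifts, applied to SDTP alone and to both arms, reporting the shift at which the conclusion changes; other pattern mixture forms would also serve if their identifying assumptions are written down. Keep the comparisons of missingness between arms, and between those who stay and leave, as description only.

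The cost is a short added specification, including the shift range and identifying assumptions, and one extra analysis. The sample size and significance level do not change.
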